Helping patients find effective strategies for dealing with chemotherapy is an important task for nurses. Complementary interventions to pharmacological treatment aim to reduce suffering at different stages of treatment.

Based on these scenario, we seek therefore produce and study an image database and validate them scientifically, aiming initially the care settings, in order to produce well-being for patients undergoing chemotherapy, as well as deepen our knowledge of man-nature connection, from the perspective of care, self-care and preservation.

2. Objectives

Verify the therapeutic potential of the validated images in the reduction of negative mood states and increase of positive states of patients undergoing the chemotherapy session.

Verify the therapeutic potential of the validated images in the treatmentrelated symptoms during the chemotherapy session.

Verify if the rate of connection with nature influences the impact in the study outcomes.

3. Design and methods

The previously validated e-Natureza image bank consists of licensed images by nature photographers who volunteered to contribute to the development of the project. They are photos with predominance of flowers, colorful birds, white birds, landscapes, photos with predominance of trees, predominating the element water, with predominance of sky, photos related to the sea, totaling 480 images.

The final image bank consists of the validated images that reached the low alert and high valence scores, that is, photos that were concentrated in the lower right quadrant of the figure below, with a view to promoting well-being and tranquility.

[figure not shown]

Figure 1 - Distribution of 360 images of International Affective Picture System (IAPS).

The randomized clinical trial will be conducted at the same institution, Albert Einstein Hospital, that the nature images were validated. The date collection of the clinical trial will be done in a period of 12 months, together with a convenience sample of patients, of both sexes, who is over 18 (eighteen), with clinical conditions and communication systems preserved, in other words, lucid, that allows the participation in the study and who are undergoing the first session of the chemotherapy treatment (most patients in the first session, have an altered emotional state, be it for fear, anxiety) independently of the type of oncological disease.

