The patients, after understood and signed the Informed Consent Form will respond to a questionnaire with sociodemographic and clinics variables (gender, age, marital status, schooling, profession, relationship with nature, diagnosis, treatment time, protocol type) for characterization of the sample (Appendix I).

The patients will be allocated randomly into two groups: 1) control and 2) intervention group through Randomizer® software.

After thirty minutes of the start of the chemotherapy session, the patient you will receive a notebook (specific to the study and blocked for other functions) that he can watch a presentation of nature images. It will be four videos with fifteen minutes each one.

At the beginning and at the end of the chemotherapy session, each patient will make an assessment of the positive and negative affects and the physical and psychological symptoms related to that chemotherapy session.

According to Paschoal and Tamayo (2008), measures of affection reflect how much the person feels enthusiastic, alert and active. The negative affect reflects how much the person feels displeasure and distress. According to these authors, one of the main affective measures used in study of general well-being is the Positive Affect/Negative Affect Scale, which through 20 words that describe feelings that should be answered on a five-point scale: "very little or nothing", "a little", " moderately", " too much", and "excessively", allowing use as a measure of state or trace. In Brazil, PANAS (Annex I) was adapted for the adult population by Giacomoni and Hutz and for adolescents by Segabinaz et al (2013), already validated elderly people in a virtual environment.

The evaluation of symptoms during the chemotherapy session also will be evaluated by - Edmonton Symptom Assessment Scale – ESASBr - (Annex II).

The Edmonton Symptom Assessment System (ESAS) is a widely used multi-symptom assessment tool, developed for the first time in 1991 by Bruera et al. to audit the symptoms of patients receiving palliative care. The ESAS is a viable, valid and reliable multi-symptom assessment tool for use in Brazil (Paiva, et al, 2015).

The participants will also respond pre intervention to the Nature Connection Scale and Nature Relatedness Scale (Annex III and IV) because it is a variable that can interfere in the study's outcomes of interest.

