The control group will undergo the same evaluations as the intervention group and at the same time interval during the chemotherapy session.

All evaluations will be performed in only one chemotherapy session.

4. Statistical analysis plan

Descriptive statistics will be applied to sociodemographic and clinical data of the study, with calculation of means and standard deviation.

By means of inferential statistics, a comparison will be made between the states subsequently presented by the patients in the clinical trial, using SPSS statistical software. For analysis correlation will be used the Spearman and Pearson tests; for averages comparison if the sample is normal, the paired t-test will be used; for nonparametric sample the Wilcoxon test, and the Fisher and chi-square tests for compare proportions. The tests will be considered significant when p <0.05.

5. History of changes

- Research Project- Version 1- submitted to Research Ethics Committee of the Hospital Israelita Albert Einstein in December 23, 2016;
- Informed Consent Form Patient- Version 1- submitted to Research Ethics Committee of the Hospital Israelita Albert Einstein in December 23, 2016;
- Documentation approved by the Research Ethics Committee of the Hospital Israelita Albert Einstein in the first version at a meeting held in 01/31/2017.
- Documentation disapproved by ClinicalTrials.gov in the first version in 03/16/2017;
- Documentation disapproved by ClinicalTrials.gov in the second version in 03/28/2018;
- Documentation disapproved by ClinicalTrials.gov in the third version in 04/16/2018.

6. Research ethics committee original report translated to English*

*The original one is in Portuguese

HOSPITAL ISRAELITA ALBERT EINSTEIN- SP

CONSUBSTANTIATED TECHNICAL ADVICE OF RESEARCH ETHICS COMMITTEE

RESEARCH PROJECT DATA

Research title: e-Natureza: Affective Validation of Nature Images as a Complementary Resource for Promoting Well-being in Hospital Environment

Researcher: [name]

Thematic area:

Version: 1

CAAE: 64096816.9.0000.0071.

Proponent institution: Hospital Israelita Albert Einstein-SP

Principal Sponsor: Hospital Israelita Albert Einstein-SP

TECHNICAL ADVICE DATA

Technical advice number: 1.906.315

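### Section 4 names no method that adjusts the between-arm comparison for the start-of-session PANAS and ESAS scores collected in every patient

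*Combined protocol and SAP*

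**What the plan says.** Section 3 (Design and methods) sets up a baseline for each outcome: "At the beginning and at the end of the chemotherapy session, each patient will make an assessment of the positive and negative affects". The same sentence covers the symptom assessment, for which ESAS is the instrument. Patients are randomised: "The patients will be allocated randomly into two groups: 1) control and 2) intervention group through Randomizer® software". The lines just before the section 4 heading extend the schedule to controls: "The control group will undergo the same evaluations as the intervention group and at the same time interval during the chemotherapy session". Each patient in either arm should therefore have a start and an end value for every score.

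Section 3 also collects two nature-connection scales before the intervention, "because it is a variable that can interfere in the study's outcomes of interest". The third objective in section 2 is "Verify if the rate of connection with nature influences the impact in the study outcomes".

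Section 4 (Statistical analysis plan) states that "a comparison will be made between the states subsequently presented by the patients in the clinical trial". For continuous scores it says "for averages comparison if the sample is normal, the paired t-test will be used", with Wilcoxon as the alternative; it does not say whether that means the signed-rank or the rank-sum version. The other methods are Pearson and Spearman correlation, and Fisher and chi-square for proportions. ANCOVA, regression, mixed models and stratified analyses are not mentioned.

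**The concern.** The start-of-session score is usually the best available predictor of the same score at the end of the session. The plan collects it in both arms, but nothing listed in section 4 can carry it into a comparison between arms. The paired t-test, and Wilcoxon if signed-rank is meant, use the start score only to test change within one group. A rank-sum test, Fisher and chi-square take no covariate. A correlation describes an association and does not adjust an arm difference.

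Two things are at stake. The first is precision: variation in end scores that the start scores explain stays in the error term, or is removed inefficiently by subtraction. The second is chance imbalance: if the arms happen to differ in mood or symptoms at session start, an unadjusted estimate carries part of that difference. Simply adding a two-sample test of end or change scores would supply a between-arm test but leave both problems in place.

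**Working it through.** The documents available contain no power, SD, effect size or start-end correlation, so there is no plan figure to reproduce. The check uses standard large-sample variances.

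**Inputs from the documents:** two randomised arms; each outcome measured at start and end in both arms; significance at p < 0.05.

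**Assumptions, not in the documents:** start-end correlation ρ from 0.3 to 0.7; equal SD at start and end; 1:1 allocation; two-sided testing. For the power illustration only: 40 per arm and a true difference of 0.5 SD.

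**Variance of the arm difference, relative to comparing end scores (= 1):**
- change scores: 2(1 − ρ)
- ANCOVA on the start score: 1 − ρ²
- ANCOVA relative to change scores: (1 − ρ²) / [2(1 − ρ)] = (1 + ρ)/2

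| ρ | change vs end | ANCOVA vs end | ANCOVA vs change |
|---|---|---|---|
| 0.3 | 1.40 | 0.91 | 0.65 |
| 0.5 | 1.00 | 0.75 | 0.75 |
| 0.6 | 0.80 | 0.64 | 0.80 |
| 0.7 | 0.60 | 0.51 | 0.85 |

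ANCOVA has the smaller variance in every row. Which of the two unadjusted analyses is better depends on ρ: change scores are worse than end scores below 0.5 and better above it.

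**Power illustration at ρ = 0.6 (normal approximation).** The standard error with SD 1 is √(2/40) = 0.2236.
- End scores: 0.5/0.2236 − 1.96 = 0.28, power about 61%.
- Change scores, SD √0.8 = 0.894: 0.5/(0.894 × 0.2236) − 1.96 = 0.54, power about 71%.
- ANCOVA, SD √0.64 = 0.8: 0.5/(0.8 × 0.2236) − 1.96 = 0.84, power about 80%.

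At ρ = 0.3 the gain over end scores is small. The ANCOVA SD is √0.91 = 0.954, and 0.5/(0.954 × 0.2236) − 1.96 = 0.38, so power is about 65% against 61%.

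**Chance imbalance, same illustration.** A start-score gap above 0.3 SD in either direction corresponds to 0.3/0.2236 = 1.34 standard errors, a probability of about 18%. At ρ = 0.6 a 0.3 SD gap shifts an end-score difference by 0.6 × 0.3 = 0.18 SD, which is 36% of the assumed 0.5 SD effect. It shifts a change-score difference by (1 − 0.6) × 0.3 = 0.12 SD in the opposite direction. ANCOVA removes this part.

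**Nature connection.** With an assumed partial correlation of 0.1 to 0.3 beyond the start score, adding it multiplies the variance by 1 − 0.1² = 0.99 to 1 − 0.3² = 0.91.

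**The case against.** The strongest reply is that randomisation already makes an unadjusted comparison valid, and that its standard error already allows for chance imbalance. That is correct. This is a point about efficiency, not bias, and its size cannot be fixed from the documents. Both instruments ask how the patient feels at the moment of completion, and section 3 expects an altered emotional state at the first session, so a modest correlation is plausible.

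Three stronger readings are tempting and should not be adopted.

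- A reader might infer that the plan compares end scores only, so that the full loss against end scores applies (61% versus 80% in the illustration). The wording about later states is ambiguous, and the test named beside it for means is paired, which works on start-to-end change. If change scores are intended, the illustrative gain is from 71% to 80%.
- A reader might infer that the sample is capped by the recruitment window with no target, making adjustment the only free source of precision. Section 3 says "The date collection of the clinical trial will be done in a period of 12 months, together with a convenience sample of patients", but not that this period fixes the number of patients. Part of the document is not available here, so the absence of a sample size cannot be asserted.
- A reader might give nature connection equal weight, because section 3 says it can affect the outcomes. Its likely contribution to precision is small. The third objective asks whether it alters the effect, which a main-effect covariate does not answer.

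It can also be said that this overlaps with section 4's failure to name a clear between-arm test for the scores. One rewritten paragraph would indeed settle both, but adding an unadjusted two-sample test would settle only that other gap.

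**Conclusion.** The point holds as a gap in the analysis plan. Section 4 names no method that yields an arm difference adjusted for the start-of-session PANAS and ESAS scores, although these are planned in every patient. The direction of the gain is secure: in large samples ANCOVA has lower variance than an end-score comparison for any non-zero correlation, and lower variance than a change-score comparison for any correlation below 1. The amount is not known. Over the assumed correlation range of 0.3 to 0.7 the variance reduction is 9% to 49% against end scores and 35% to 15% against change scores. The power figures are illustrations resting on an assumed 40 per arm, 0.5 SD and correlation of 0.6. The documents do not support calling an unadjusted analysis invalid. The change is worth making because it uses data already planned and fixes one main contrast before end, change and adjusted results can be compared with each other.

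**What to change.** In section 4, make the main between-arm analysis a linear model for each outcome: end-of-session score = arm + the same score at session start. Report the adjusted arm difference with its 95% CI. The outcomes are PANAS positive affect, PANAS negative affect, and either each ESAS item or an ESAS total. Annex II shows separate 0 to 10 items and the documents available define no total, so that choice must be made and written down in advance.

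For skewed scores, which are likely for symptom items with many zeros, specify a rank-based ANCOVA or a bootstrap confidence interval as a sensitivity analysis.

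Add nature connection as a covariate only if one of the two scales is named beforehand. Address the third objective separately, with an arm-by-connection interaction.

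The cost is a paragraph of SAP text and one or two degrees of freedom per model. No new data, patients or visits are needed, and SPSS, already the named software, fits the linear model.

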Annex III

Connectedness to nature scale*- Mayer and Frantz, 2004

Please answer each of these questions in terms of *the way you generally feel*. There are no right or wrong answers. Using the following scale, in the space provided next to each question simply state as honestly and candidly as you can what you are presently experiencing.

1	2	3	4	5
Strongly		Neutral		Strongly agree
disagree				
1.	I often feel a sense	of oneness with the nat	aral world around me	
2.	I think of the natu	ral world as a communi	y to which I belong.	
3.	I recognize and ap	preciate the intelligence	of other living organis	sms.
4.	I often feel discon	nected from nature.		
1. 2. 3. 4. 5. 6. 7. 8. 9. 10. 11.	When I think of n	ny life, I imagine myself	o be part of a larger of	cyclical process of living.
6.	I often feel a kinsl	ip with animals and play	its.	
7.	I feel as though I	belong to the Earth as ec	jually as it belongs to	me.
8.	I have a deep und	erstanding of how my ac	tions affect the natura	ıl world.
9.	I often feel part of			
10.	I feel that all inha	bitants of Earth, human,	and nonhuman, share	e a common 'life force'.
	Like a tree can be	part of a forest, I feel er	nbedded within the br	roader natural world.
12.	When I think of n	y place on Earth, I cons	ider myself to be a top	p member of a hierarchy that exists in
	nature.			
13.	I often feel like I a	m only a small part of the	natural world around	I me, and that I am no more important
	than the grass on	the ground or the birds i	n the trees.	
14.	My personal welfa	re is independent of the	welfare of the natural	world.

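### Objective 3, whether connection with nature influences the impact, has no assigned analysis, and no listed method tests whether the difference between arms depends on connection

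*Combined protocol and SAP*

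**What the plan says.** Section 2 lists three objectives. The first two concern mood states and treatment-related symptoms. The third is to "Verify if the rate of connection with nature influences the impact in the study outcomes".

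Section 3 randomises patients to control or intervention and measures affect (PANAS) and symptoms (ESAS) at the start and end of one chemotherapy session. On connection it says: "The participants will also respond pre intervention to the Nature Connection Scale and Nature Relatedness Scale". The reason given is "because it is a variable that can interfere in the study's outcomes of interest". Controls are covered too: "The control group will undergo the same evaluations as the intervention group".

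Section 4 says that "a comparison will be made between the states subsequently presented by the patients in the clinical trial" and then lists methods. For correlation it says only: "For analysis correlation will be used the Spearman and Pearson tests". The others are the paired t-test, the Wilcoxon test, and Fisher and chi-square tests for proportions, at p < 0.05. It mentions neither connection scale and ties no method to Objective 3.

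**The concern.** In a randomised two-arm trial the impact of the images is the difference between arms. A factor that influences that impact is an effect modifier, and showing this requires comparing the arm difference across levels of connection. Section 4 contains nothing that does so: no interaction term, no regression model, no comparison of slopes between arms.

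If the listed correlation fills the gap, patients who feel closer to nature may simply report better mood whether or not they see the images. That prognostic association could then be reported as connection shaping the effect of the images. Whether this happens would depend on the scale, the outcome form (end score or change) and the arms, all of which stay open until the data are in hand.

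**Working it through.** **Objective against methods.** Section 4 has no figure to reproduce, so the first check sets each listed method beside the question.

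- Paired t-test and Wilcoxon signed-rank: within-patient change, with no connection score. If Wilcoxon means the rank-sum test, it compares two groups, still without connection.
- Fisher and chi-square: proportions. They do not test whether an arm difference varies with a baseline score.
- Pearson and Spearman: association between two scores in one set of patients. They can involve connection but not the arm difference.

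**Size, under assumptions.** The documents give no sample size, SD or correlation. Assumed: 30/50/100 per arm, normal scores with SD 1, start-end correlation 0.6, two-sided 0.05, equal arm means. The percentages come from 10,000 simulated trials per cell. Approximate formulas are shown as a check.

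*(a) No modification; connection correlates 0.3 with change in both arms and 0 with the start score.* Power of a correlation is about Φ(atanh(r)·√(n−3) − 1.96). At n = 50: 0.3095 × 6.856 = 2.122, and Φ(0.162) = 56%. Simulated image-arm correlation with change: 38/58/86%. Pooled over both arms: 65/87/99%.

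*(b) No modification; connection correlates 0.3 with the start and end scores alike.* This is plausible for a trait, and Annex III asks about "the way you generally feel", although the same instruction also asks for present experience. The covariance with change is 0.3 − 0.3 = 0, so the false signal disappears: about 5/5/5%. With the end score it returns: image arm 37/58/87%, pooled 66/87/99%. Over r = 0.1/0.2/0.3/0.4 at 50 per arm, the image-arm end-score correlation is significant in 10/29/57/84%, and the change correlation in about 5% throughout.

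*Interaction test.* The model is end score on start score, arm, connection and arm-by-connection. Over all no-modification cells it rejects in 4.6 to 5.4%.

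*Real modification (r with change 0.3 with images, 0 in control).* The SD of change is √(2 − 2×0.6) = 0.894, so the slope is 0.3 × 0.894 = 0.268 in the image arm and 0 in control. Residual variances are 1 − 0.36 − 0.072 = 0.568 and 1 − 0.36 = 0.640. At 50 per arm the SE of the interaction is about √((0.568 + 0.640)/47) = 0.160. The ratio is 0.268/0.160 = 1.67 and the power about Φ(1.67 − 1.985) = 38%. Simulated: 24/39/67%. The image-arm correlation with change is significant in 37/57/86%, about the same as in (a), where there is no modification. It cannot tell the two apart.

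**Other uses of correlation.** A separate simulation (4,000 trials per cell, residual SD 1, arm effect 0.3) gives two more results. With equal slopes of 0.3 in both arms, exactly one arm's correlation is significant in 45/49/28% of trials, so comparing significance between arms is no substitute. With opposite slopes (−0.25 control, +0.25 images), a pooled correlation is significant in only 5 to 6%, against 45/67/93% for the interaction term.

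**The case against.** **The objective may mean only an association.** Section 3 says connection can interfere in the outcomes. Section 1 asks whether people more related to nature rate nature images more positively. Specific objective 4 in the ethics committee report (section 6) uses the same idea of influence for the image validation phase, which as described has no treatment arms. The trial-phase objectives in that report (6 to 8) do not mention connection. On this reading correlation is suitable, and what is missing is the scale, outcome and arms. This stands as a possible reading. It does not displace the plainer one, because Objective 3 speaks of influence on the impact, not on the outcomes alone.

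**The harm is conditional.** Scenario (a) needs connection to track mood change in controls who see no images, and nothing in the documents shows this. In (b), correlating change keeps the 5% error rate. If connection is truly unrelated to change in controls, the image-arm change correlation is valid and detects modification more often than the interaction (37/57/86% against 24/39/67%). All of this stands, but that advantage rests on an assumption only the control arm can check. Once controls enter, the comparison of arms is the interaction.

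**The remedy has weaknesses.** PANAS and 0-10 ESAS scores are bounded. Robust standard errors allow for unequal variance, but a floor effect can still create or hide an interaction, and the simulations used normal scores. The test count must also include the second scale. Both are carried into the fix.

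A reader might infer that the plan commits to correlation for Objective 3. It does not: no variables are named, and that use is an inference.

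**Conclusion.** The point holds in this form. Objective 3 has no assigned analysis, and no listed method tests whether the arm difference depends on connection. Section 4 can be read whole, between sections 3 and 5. A few pages after the objectives in the ethics report were not available, and the finding does not rest on them.

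If a single correlation is used, the chance of a significant result without any modification runs from about 5% to about 57% at 50 per arm in the image arm with r = 0.3, and to about 87% pooled. It depends on unstated choices and on how connection relates to start and end mood. These are illustrations under assumed inputs, not forecasts.

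Two stronger inferences are not supported. One is that a false claim of effect modification is inevitable: scenario (b) with change shows otherwise. The other is that the main comparisons are compromised: Objectives 1 and 2 do not depend on this analysis. The gap matters because a stated objective could be answered with a method that does not address it, when the data for a better one are already collected in both arms.

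**What to change.** Add one paragraph to section 4:

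> Objective 3 asks whether the effect of the images differs by connection with nature. For PANAS positive affect, PANAS negative affect and each ESAS item, the end-of-session score will be modelled linearly on start-of-session score, arm, pre-intervention connection score (continuous) and arm-by-connection, using both arms and robust standard errors because the scores are bounded. The interaction coefficient and its 95% CI will be reported as exploratory. One connection scale, named here before analysis, is the moderator; the other is a sensitivity analysis. Correlations are descriptive only.

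Strong floor or ceiling effects should be reported beside the interaction, since robust errors do not remove them.

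**Cost.** One paragraph and one model the plan does not now contain. Both scales and both outcome assessments are already collected in both arms.

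**Downsides.**

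- *Precision.* Under the assumptions above, with ordinary standard errors, the 95% CI half-width is about 0.42/0.31/0.22 end-score SD per SD of connection at 30/50/100 per arm. It ranges from 0.49/0.37/0.25 at start-end correlation 0.4 to 0.31/0.23/0.16 at 0.8. Power for r = 0.3 against 0 is 24/39/67%, so a non-significant interaction should not be read as no modification.
- *Multiplicity.* Two PANAS scores and the nine ESAS rows shown in Annex II make 11 tests: 1 − 0.95^11 = 43% chance of at least one false positive if independent. With both scales, 22 tests give 1 − 0.95^22 = 68%; the scales are probably correlated, so this is only a guide. Hence the exploratory label.

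If only an association is intended, Objective 3 should say so and section 4 should name the scale, outcome and arms. That would make the text consistent but would not tell anyone whether the images work differently by connection.

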It is common to all these bases: formal access required, exclusive to researchers, for use restricted to scientific studies, without commercial use. The images can not be published and all the banks are asymmetrical, formed more by negative than positive images. These banks, therefore, are unique to research and can not be used in clinical practice, the main reason for the realization of the present study. In the hospital context, our interest also falls on images that have the potential to promote states of well-being and comfort.

Besides knowing, the emotional responses, another relevant aspect to be questioned is if individuals more related to nature evaluate more positively the images of nature. On the other hand, exposure to images of nature can increase the feeling of connection with nature? Knowing this relationship is of particular importance not only for the use of images of nature as a potential resource of balance for human health, but also for uncovering ways to improve the man-nature relationship, in order to preserve it as well, thus expanding the relevance of the production and dissemination of validated images.

There are clinical situations for which we believe that interventions based on nature may be particularly useful, among them, when patients undergo chemotherapy.

Chemotherapy can cause a crisis in the patient's life, with physical and psychic impacts. In clinical use it is generally well tolerated by patients and moderate side effects are well controlled with appropriate dosages and judicious use of other drugs such as antiemetic's (Sawada, 2009).

On the other hand, emotional aspects can be ignored and more difficult to control. Some emotional reactions such as anxiety, depression and emotional distress can be observed during chemotherapy (Baker-Glenn, et al., 2010). Infusion time can be very distressing, but it can also be seen and experienced as a period of seclusion and rest. For many patients it is distressing because it can mean imprisonment or incapacitation to perform the tasks. He also appeals to discourse of boredom, lack of what to do (Sette, Gradvohl, 2014). Some researchers concluded that levels of emotional distress during chemotherapy are high, suggesting a clinical need for interventions to provide support to patients during chemotherapy (Decat et al., 2010).

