Annex II

Edmonton Symptom Assessment Scale – ESASBr

This is a symptom assessment scale. You will respond to 10 items with responses ranging from 0 (minimum intensity) to 10 (maximum intensity). Please circle the number that best describes your symptoms AT THIS TIME.

No pain	0	1	2	3	4	5	6	7	8	9	10	Worst possible pain
Not tired	0	1	2	3	4	5	6	7	8	9	10	Worst possible tiredness
Not nauseated	0	1	2	3	4	5	6	7	8	9	10	Worst possible nausea
Not depressed	0	1	2	3	4	5	6	7	8	9	10	Worst possible depression
Not anxious	0	1	2	3	4	5	6	7	8	9	10	Worst possible anxiety
Not drowsy	0	1	2	3	4	5	6	7	8	9	10	Worst possible drowsiness
Best appetite	0	1	2	3	4	5	6	7	8	9	10	Worst possible appetite
Best feeling of wellbeing	0	1	2	3	4	5	6	7	8	9	10	Worst possible feeling of wellbeing
No shortness of breath	0	1	2	3	4	5	6	7	8	9	10	Worst possible shortness of breath

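### Section 4 names no test that compares the randomised arms on PANAS or ESAS; for normal data it names only the paired t-test, which cannot separate an image effect from a change common to both arms.

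*Combined protocol and SAP*

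**What the plan says.** Section 3 (Design and methods) sets up a parallel-group trial: "The patients will be allocated randomly into two groups", control and intervention. Each patient completes PANAS and ESAS at the start and end of a single session. Control is measured in the same way: "The control group will undergo the same evaluations as the intervention group and at the same time interval during the chemotherapy session".

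Section 4 (Statistical analysis plan) describes the inference in general terms: "a comparison will be made between the states subsequently presented by the patients in the clinical trial". It then lists the tests:

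- Spearman and Pearson for correlation.
- For means, "for averages comparison if the sample is normal, the paired t-test will be used; for nonparametric sample the Wilcoxon test".
- Fisher and chi-square for proportions.

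The decision rule is "The tests will be considered significant when p <0.05". Section 4 names no independent-samples t-test, Mann-Whitney test, ANCOVA, mixed model or group-by-time interaction, and it does not mention the arms.

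**The concern.** The first two objectives in Section 2 concern what the images do to mood and symptoms. Only the contrast with control answers that. A before/after test within the image arm measures the image effect plus everything else that happens during the session.

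The protocol gives reason to expect something else to happen, in either direction. Section 3 justifies recruiting at the first session because "most patients in the first session, have an altered emotional state, be it for fear, anxiety", and such a state may ease as the session passes. Section 1 notes that "Infusion time can be very distressing, but it can also be seen and experienced as a period of seclusion and rest". If both arms improve, the images could be credited with it. If both worsen, a real benefit could be cancelled in the before/after comparison.

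**Working it through.** **Which listed test could compare the arms?**

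| Test in Section 4 | Compares the arms on PANAS or ESAS? |
|---|---|
| Paired t-test | No. It needs two scores from the same or matched patients; the arms are unmatched. |
| Wilcoxon test, unqualified | Not specified. Signed-rank is paired, rank-sum is between groups. As the stated counterpart of the paired t-test, signed-rank is the natural reading. |
| Fisher, chi-square | Proportions only. ESAS items run 0 to 10 and PANAS items are on five points; no responder cut-off is defined. |
| Spearman, Pearson | No. They measure association. |

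**Inputs for the illustration.** From the documents: significance at p < 0.05, two arms, two assessments. Assumed, because the documents do not give them: two-sided tests, 1:1 allocation, *n* = 20 to 100 per arm, normally distributed changes, and shifts expressed in SDs of the change score. The plan has no figure of its own to reproduce.

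**1. False positives: no image effect, common shift *c*.** The image-arm paired t statistic is noncentral t with *n* − 1 degrees of freedom and noncentrality *c*√*n*. Example: *c* = 0.3 and *n* = 50 give 0.3 × √50 = 2.12 against a critical value of 2.01, so P(significant) = 54.8%.

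| Common shift | n = 20 | n = 30 | n = 50 | n = 100 |
|---|---|---|---|---|
| 0 | 5.0% | 5.0% | 5.0% | 5.0% |
| 0.2 SD | 13.6% | 18.5% | 28.4% | 50.8% |
| 0.3 SD | 24.7% | 35.5% | 54.8% | 84.4% |
| 0.5 SD | 56.5% | 75.4% | 93.4% | 99.9% |

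Over shifts of 0, 0.2, 0.3 and 0.5 SD and all four sizes, simulated between-arm tests (20,000 runs per cell, pre/post correlation 0.5) stayed at 4.6–5.2% for the t-test on change and 4.7–5.2% for ANCOVA.

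**2. Using both arms informally.** Suppose the claim requires a favourable significant change with images and no significant change in control. With independent arms the probability is P(favourable, significant) × (1 − P(significant)). Example: 0.3 SD and *n* = 50 give 0.548 × (1 − 0.548) = 24.8%.

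| Common shift | n = 20 | n = 30 | n = 50 | n = 100 |
|---|---|---|---|---|
| 0.2 SD | 11.5% | 15.0% | 20.3% | 25.0% |
| 0.3 SD | 18.6% | 22.9% | 24.8% | 13.2% |

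The product *p*(1 − *p*) cannot exceed 25%, which is the ceiling for this rule.

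**3. The Wilcoxon ambiguity.** No image effect, common shift 0.3 SD, *n* = 30, 50 and 100 (3,000 simulated runs). Signed-rank in the image arm rejects in 34.7%, 53.9% and 82.2%. Rank-sum between arms rejects in 4.5–5.2%, whether applied to end scores or to changes.

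**4. Hidden benefit.** Common worsening of 0.5 SD, image benefit of 0.5 SD, *n* = 50.

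- Image-arm paired test: the net change is −0.5 + 0.5 = 0, so it rejects in 5%.
- Between-arm t-test on change: noncentrality 0.5 × √(50/2) = 2.5 on 98 degrees of freedom; power 70%.
- ANCOVA with pre/post correlation 0.5 and equal SDs: the SD of the change equals the SD of a score, because √(2(1 − 0.5)) = 1. The residual SD is √(1 − 0.25) = 0.866 of it. Noncentrality is (0.5/0.866) × 5 = 2.89; power about 81%.

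**The case against.** The strongest reply is that the plan is terse, and does not mean to ignore control. Patients are randomised, control is measured identically, and the general sentence in Section 4 does not restrict the comparison to one arm. The Wilcoxon test may mean rank-sum, and that branch could well be the one used, since the items are bounded integers. A team holding control data would also run the paired test there and see a common shift in both arms, so the image-arm percentages describe a rule the plan never states. Likewise the benefit in step 4 is hidden only if control is ignored: at 50 per arm, worsening in control without a significant change in the image arm would appear in about 0.934 × 0.95 = 89% of trials.

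Part of this stands. The figures in steps 1 and 4 are the worst-case reading, the rank-sum reading cannot be excluded, and the common shift is inferred from the protocol's description of patients; it is not a measured change. None of it supplies a test. The general sentence names no arm and no contrast. Rank-sum would cover only non-normal data. Setting two within-arm p-values side by side is not a valid comparison of arms and, by step 2, can reach a false-positive rate of about 25%. If the team intends to compare the arms by some other test, that test would be chosen after the data are seen.

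A further objection is that the repair leaves multiplicity open. Two PANAS scores and the nine ESAS rows legible in Annex II make 11 tests; if independent, 1 − 0.95^11 = 43% chance of at least one false positive. That is true, but the current plan has the same problem and the repair does not add to it.

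**Conclusion.** The concern holds and must be fixed. No test in Section 4 is specified as a comparison of the randomised arms on PANAS or ESAS, and the one test named for normally distributed scores cannot make that comparison. This is a wrong test for the stated objective, not only missing detail.

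The consequence depends on how the within-arm results would be read. With a common shift of 0.2 to 0.3 SD and 20 to 100 per arm, a null intervention would look effective in 13.6% to 84.4% of trials if the image arm is read alone, and in 11.5% to 25.0% if non-significance in control is also required. A between-arm test gives 5%. These figures rest on assumed sample sizes and shifts and are not estimates for this trial. With no common shift, the image-arm test also stays at 5%. The defect itself does not depend on the assumptions.

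**What to change.** Replace the sentence on comparing averages with one prespecified between-arm analysis, for example:

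> For PANAS positive affect, PANAS negative affect and [each ESAS item, or an ESAS total defined here], the end-of-session score will be compared between the randomised arms by ANCOVA, with arm as factor and the start-of-session score as covariate. The adjusted mean difference and its 95% CI will be reported. A rank-based between-arm analysis will be the sensitivity analysis; the test will not be chosen by a normality check. Within-arm changes will be descriptive only.

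Any valid between-arm test, such as an independent-samples test on change scores, cures the core defect. ANCOVA is preferred because it is usually more precise. If a Wilcoxon test is kept, state which one and what it compares.

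The cost is small. Both arms already provide start and end scores, and SPSS runs ANCOVA. One decision must come first: whether ESAS is analysed by item or as a total. Annex II says "You will respond to 10 items with responses ranging from 0 (minimum intensity) to 10 (maximum intensity", and neither it nor Section 3 defines a total. The sponsor should expect the between-arm p-value usually to be less favourable than the within-arm one.
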